11.4 Health Economic Analysis

The health economic analysis will estimate the cost per POC multiplex PCR test and the cost per conventional blood culture. A costing exercise of the resources used to test patients via each route will be undertaken in 5% of samples. The personnel involved in taking the samples will record details of their time and the consumables used. Costs will be obtained directly from the manufacturer for the Multiplex PCR testing equipment and disposables. Unit costs will be applied from national sources such as the NHS reference costs and the Personal Social Services Research Unit (PSSRU) Costs of Health and Social Care.

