4.3 Study Objectives

4.3.1 Primary Objective:

The primary objective of this study is measurement of the sensitivity, specificity, positive predictive value and negative predictive value of this novel test, in comparison with conventional culture, in critically ill adults with suspected sepsis.

4.3.2 Secondary Objectives:

The secondary objectives of this study are:

- (i) To estimate the true cost per test for conventional blood culture and for multiplex PCR
- (ii) To estimate the time to result for conventional blood culture and for multiplex PCR

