9.2 Study Procedures

9.2.1 Blood Sampling

Blood cultures will be taken in the usual manner, for the participating study site, in the course of routine care. At the time that each blood culture is taken from an eligible patient, a 5ml sample of blood will also be collected for multiplex PCR testing. An additional 10ml sample of blood will also be collected where

- (i) it is the first sample
- (ii) research staff are available to process and store the sample

In patients meeting these criteria, and where resources permit, a further 3ml sample of blood will be taken into RNA preservation reagent (Tempus) tubes.

The research blood will be obtained from the same sampling event as the matched blood culture (i.e. from the same syringe draw); if this is not possible then research blood should be obtained by the same sampling technique (i.e. venepuncture or accessing the same vascular device).

When multiple sampling sites are being used for routine clinical blood cultures at the same time, the peripheral (venepuncture) sample is preferred for matched sampling in this study. If a peripheral sample is not being obtained in routine clinical care, then obtaining matched research and routine culture samples from a vascular access device is acceptable.

At participating sites in England, Wales and Northern Ireland, patients undergoing blood culture in the course of routine clinical care will have a research blood sample taken at the same time. The research blood sample will be stored pending informed consent/assent being obtained within 72 hours of taking the sample. No research blood samples will be tested until consent/assent for participation in this study has been obtained. In the event that consent/assent is not obtained the entire research sample will be discarded with no research tests being carried out on it.

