9.2.2.1 Sample for Multiplex PCR Testing

Approximately the first half of the study samples will be initially stored at site and transferred in batches to a central laboratory in Queen's University Belfast, for testing using the Multiplex PCR device, in accordance with the Sample Processing Guideline. Subsequent samples will be analysed using the Multiplex PCR device at the POC by ICU clinical and/or research and/or technical staff at participating sites who have received training in the use of the Multiplex PCR testing device and transferred in batches to a central laboratory in Queen's University Belfast for testing using the Multiplex PCR device.

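### Section 11.4 has only the staff who take the blood record their time, so the cost per POC PCR test may be understated by unrecorded device-operator time

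*Protocol*

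**What the plan says.** The first secondary objective (Protocol 4.3.2) is "To estimate the true cost per test for conventional blood culture and for multiplex PCR". Section 11.4 turns this into an analysis: "The health economic analysis will estimate the cost per POC multiplex PCR test and the cost per conventional blood culture". It sets the scope widely: "A costing exercise of the resources used to test patients via each route will be undertaken in 5% of samples". It then says who collects the data: "The personnel involved in taking the samples will record details of their time and the consumables used". Two sources of prices follow. For PCR, "Costs will be obtained directly from the manufacturer for the Multiplex PCR testing equipment and disposables". In general, "Unit costs will be applied from national sources such as the NHS reference costs" and the PSSRU unit costs.

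Three other parts of the protocol bear on this:

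- **9.2.1, the draw.** "The research blood will be obtained from the same sampling event as the matched blood culture", from the same syringe where possible and otherwise by the same technique.
- **9.2.2.1, the testing.** "Approximately the first half of the study samples will be initially stored at site and transferred in batches to a central laboratory". Later samples are run at the point of care by trained ICU staff, who may be clinical, research or technical, and are also sent for central testing.
- **8 and 9.2.1, consent.** In England, Wales and Northern Ireland consent is deferred. The research sample is held for up to 72 hours and may not be tested until consent or assent is in place.

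**The concern.** A cost per test needs the quantities of each resource as well as their prices. The one group told to record quantities is present at a step that the two tests mostly share. Most of the difference in cost arises later: preparing the sample, loading and running the device, repeating failed runs and reading the result. For that work 11.4 names prices of equipment and disposables, but nobody to record labour. National sources can price a minute of staff time, but they cannot say how many minutes a new device takes.

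At stake is a named secondary objective that claims the true cost of each test. If operator labour drops out, the error favours the new test. These are prospective data: minutes not logged while the device is in use cannot be recovered by a later analysis plan. The primary accuracy results are not affected.

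**Working it through.** The protocol states no cost, staff time or wage, so there is no figure of its own to reproduce. The check compares sections and then uses simple arithmetic.

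**Step 1. Is operator time captured anywhere?**

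| Section | What it captures | Operator hands-on time? |
|---|---|---|
| 11.4, recording rule | Time and consumables of the staff who take the blood | Not named |
| 11.4, manufacturer prices | PCR equipment and disposables | No |
| 11.4, national sources | Unit prices | No quantities |
| 9.1, data list | Date and time the PCR test was completed | No; nor repeats or staff grade |
| 9.2.3, time to result | Time needed to complete each test | No; this is turnaround, not labour |

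**Step 2. Would the blood-taker's record include the device run anyway?** Only if the same person does both and keeps recording. Outside Scotland the sample waits for consent, so the run is a separate event that may fall up to 72 hours after the draw. Section 11.4 asks for no record at that second event. In Scotland consent may precede sampling, so the two steps could be continuous there.

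**Step 3. Which samples can inform a POC cost?**

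- Costing sample: 5% of 4501 = 0.05 × 4501 = 225.05, about 225.
- About the first half of study samples are tested only centrally. If the 5% were spread evenly over the study (an assumption, since 11.4 gives no selection rule), 225.05 / 2 = 112.5. About 113 would then involve no POC run, leaving about 113 that do.

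**Step 4. Size of the possible omission.** Omitted cost per PCR test = (operator minutes / 60) × hourly rate. Both inputs are assumptions.

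| Minutes | £20/hour | £40/hour | £60/hour |
|---|---|---|---|
| 5 | £1.67 | £3.33 | £5.00 |
| 10 | £3.33 | £6.67 | £10.00 |
| 20 | £6.67 | £13.33 | £20.00 |
| 30 | £10.00 | £20.00 | £30.00 |

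Failed or repeated runs would add to this. Section 11.3 removes a participant from all analyses when the PCR result is absent. Read literally, the resources spent on a run that gives no result would also leave the costing.

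**The case against.** The strongest reply is that 11.4 does not exclude operator time. Its scope sentence covers testing by each route, not just phlebotomy, and 5.2 likewise lists resource use associated with PCR testing. Nothing says that blood-takers and device operators are different people. The detail of a time log could sit in a costing form that is not shown. This stands to the extent that understatement cannot be stated as fact. It does not remove the point, because the only collection rule given is narrower than the scope and stops at the draw.

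A reader might go further than the text allows in four ways:

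- **That labour is counted for culture and left out for PCR.** The protocol does not say so. Recording of laboratory staff time for culture is equally absent, the unit-cost sentence is not tied to either test, and the documents do not show what the national reference costs include. If both labour items were missing, the direction of the error in the cost difference would be unknown.
- **That the blood-taker's record cannot separate the tests at all.** The research blood is an extra 5 ml, may need a separate draw, and consumables are recorded too. The sampling step is largely shared, not identical.
- **That half of the costing sample is wasted.** The 113 depends on an even spread, and centrally tested samples still inform the cost of blood culture.
- **That the pound range measures the bias.** It rests wholly on assumed minutes and wages, and the protocol gives no baseline cost to set it against.

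It is also fair that this is a descriptive secondary costing, with no cost-effectiveness model or decision threshold.

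**Conclusion.** The point holds as a conditional risk. Followed as written, 11.4 would collect staff time at a step mostly common to both tests and would not collect the hands-on time of running the POC device. The PCR cost per test would then be too low by operator minutes times wage, plus any labour spent on failed or repeated runs. The size cannot be derived from the documents; the £1.67 to £30 range is an illustration only. The conclusion assumes that sites follow the recording sentence literally and that no unseen costing form widens it. The wider claim, that the comparison between the tests is biased in favour of PCR, is not established, because the treatment of culture laboratory labour is not stated. The change is worth making now because the data cannot be collected afterwards.

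**What to change.** Amend Protocol 11.4 to say that:

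1. Staff who prepare samples and run the POC device record hands-on time, failed or repeated runs, and consumables, at the time of the run. Runs that give no result stay in the costing despite 11.3.
2. Samples used for the PCR costing are drawn from the POC phase. Samples from the central phase may still be used for the blood culture cost.
3. Culture laboratory labour is costed on the same basis as PCR labour, with its source named.

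The cost is a short log for up to about 225 samples, completed by staff already running the device. The PCR cost per test may come out less favourable.

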11.5 Additional Analysis

Planned additional analyses will be described in the statistical analysis plan.

12 DATA MONITORING

12.1 Data Access

Prior to commencement of the study, the PI will give permission for trial related monitoring, audits, ethics committee review and regulatory inspections, by providing direct access to source data and trial related documentation. Consent from patients for direct access to data will also be obtained. The patients' confidentiality will be maintained and will not be made publicly available to the extent permitted by the applicable laws and regulations.

12.2 Monitoring Arrangements

The CTU will be responsible for trial monitoring. The frequency and type of monitoring will be detailed in the monitoring plan and agreed by the trial Sponsor. On-site monitoring visits and central monitoring activities will be conducted in accordance with the trial monitoring plan. On-site monitoring will be an on-going activity from the time of initiation until trial close-out and will comply with the principles of Good Clinical Practice (GCP).

On-site monitoring visits during the trial will check the accuracy of entries on CRF's against the source documents, the adherence to the protocol, study procedures and GCP.

The PI or designee should ensure that access to all trial related documents including source documents (to confirm their consistency with CRF entries) are available during monitoring visits. The extent of source data verification (SDV) will be documented in the monitoring plan.

13. TRIAL COMMITTEES

13.1 Trial Management Arrangements

The Co-CI's will have overall responsibility for the conduct of the study. The CTU will undertake trial management including all clinical trial applications (Ethics and Research Governance), site initiation/training, monitoring, analysis and reporting. The Trial Co-ordinator will be responsible on a day to day basis for overseeing and co-ordinating the work of the multi-disciplinary trial team, and will be the main contact between the trial team (and other parties involved). Before the trial starts site training will take place to ensure that all relevant essential documents and trial supplies are in place and that site staff are fully aware of the trial protocol and procedures. The CTU will assist and facilitate in the setting up and

co-ordination of the trial committees including the Trial Management Group (TMG) and Trial Steering Committee (TSC).

13.2 Trial Management Group (TMG)

A Trial Management Group (TMG) will be established and Chaired by one of the Co-CI's. The TMG will have representation on it from the CTU and other investigators/collaborators who are involved in the study and provide trial specific expertise (e.g. trial statistician). This group will have responsibility for the day to day operational management of the trial, and regular meetings of the TMG will be held to discuss and monitor progress. The discussions of the TMG will be formally minuted and a record kept in the TMF.

A TMG Charter will be drawn up to detail the terms of reference of the TMG including roles and responsibilities.

13.3 Trial Steering Committee (TSC)

The conduct of the trial will be overseen by a TSC. The TSC is a group that act as the oversight body for the trial on behalf of the Sponsor/Funder. Throughout the trial the TSC will take responsibility for monitoring and guiding overall progress, scientific standards, operational delivery and protecting the rights and safety of trial patients.

The TSC will include an independent Chair, not less than two independent clinicians/trialists, a patient representative and the Co-CI's. Representatives of the Sponsor/Funder, Co-investigators and CTU may attend TSC meetings as observers and at the discretion of the Chair. The TSC Charter will document the membership of the committee and outline the terms of reference of the TSC including roles/responsibilities,, organisation of meetings, reporting, decision making and the relationship with the other trial committees. An inaugural meeting will be held prior to recruitment commencing. Subsequent meetings will be scheduled within 6 months of commencing recruitment and approximately annually thereafter.

14. REGULATIONS, ETHICS AND GOVERNANCE

The trial will comply with the principles of GCP, the requirements and standards set out by the applicable regulatory requirements in the UK and the Research Governance Framework.

14.1 Sponsorship

The Belfast Health and Social Care Trust (BHSCT) will act as Sponsor for the study and the Co-CI's will take overall responsibility for the conduct of the trial. Separate agreements will be put in place between the Sponsor, CI and each organisation who will undertake Sponsor delegated duties in relation to the management of the study.

14.2 Funding

This study is funded by Innovate UK. Funding provided by Innovate UK covers the costs for staff based at the Clinical Trials Unit (CTU) the trial co-ordinating centre for the study.

14.3 Indemnity

The BHSCT will provide indemnity for any negligent harm caused to patients by the design of the research protocol through the Clinical Negligence Fund in Northern Ireland.

14.4 Competing Interests

The co-CIs and members of the TMG have no financial or non-financial competing interests. The study is funded by Innovate UK and [name] and [name] are co-investigators.

14.5 Ethical Approvals

The trial will be conducted in accordance with the ethical principles that have their origin in the Declaration of Helsinki. The protocol will be approved by a Research Ethics Committee.

14.6 Good Clinical Practice

The trial will be carried out in accordance with the principles of the International Conference on Harmonisation Good Clinical Practice (ICH-GCP) guidelines (www.ich.org). All members of the trial team will be required to have completed GCP training.

14.7 Protocol Compliance

A protocol deviation is defined as an incident which deviates from the normal expectation of a particular part of the trial process. Any deviations from the protocol will be fully documented on the protocol deviation form in the CRF.

A serious breach is defined as a deviation from the trial protocol or GCP which is likely to effect to a significant degree:

- (a) the safety or physical or mental integrity of the subjects of the trial; or
- (b) the scientific value of the trial

The PI or designee is responsible for ensuring that serious breaches are reported directly to the CTU within one working day of becoming aware of the breach.

Protocol compliance will be monitored by the CTU who will undertake site visits to ensure that the trial protocol is adhered to and that necessary paperwork (e.g. CRF's, patient consent) is being completed appropriately.

14.8 Protocol Amendments

The investigators will conduct the study in compliance with the protocol given approval/favourable opinion by the Ethics Committee. Changes to the protocol may require ethics committee approval/favourable opinion prior to implementation. The CTU in collaboration with the sponsor will submit all protocol modifications to the research ethics committees for review in accordance with the governing regulations.

14.9 Patient Confidentiality

In order to maintain confidentiality, all study reports and communication regarding the study will identify the patients by the assigned unique trial identifier only. Computers where information will be stored will be password protected. Patient confidentiality will be maintained at every stage and will not be made publicly available to the extent permitted by the applicable laws and regulations.

14.10 Record Retention

The PI will be provided with an Investigator Site File (ISF) by the CTU and will maintain all trial records according to GCP and the applicable regulatory requirements. The Trial Master File (TMF) will be held by the CTU within the BHSCT and the essential documents that make up the file will be listed in an SOP. On completion of the trial, the TMF and study data will be archived by the CTU according to the applicable regulatory requirements and as required by the BHSCT Sponsor. Following confirmation from the Sponsor the CTU will notify the PI when they are no longer required to maintain the files. If the PI withdraws from the responsibility of keeping the trial records, custody must be transferred to a person willing to accept responsibility and this must be documented in writing to the CTU and Sponsor.

15. DISSEMINATION/PUBLICATIONS

15.1 Trial Publications

The final study report will be provided by the Trial Statistician; it is anticipated that the study findings will be published in national and international peer review journals which will be led by the Co-CI's. This will secure a searchable compendium of these publications and make the results readily accessible to the public and health care professionals. In addition study findings may be presented at both national and international meetings and also to appropriate patient groups.

15.2 Authorship Policy

An author will be considered to be someone who has made a substantive intellectual contribution to the study. All investigators, Trial Statistician and relevant members of the Trial Management Group are potential co-authors. Collaborators will be acknowledged.

15.3 Trial Registration

The trial will be registered with the UK Medicines and Healthcare products Regulatory Agency (MHRA) as a diagnostic accuracy study of a medical device and with the International Standard Randomised Controlled Trial Registry (ISRCTN).

15.4 Data Sharing Statement

Requests for data sharing will be reviewed on an individual basis by the Co-CI and TMG.

15.5 Data Access

Following the publication of the primary and secondary outcomes there may be scope to conduct additional analyses on the data collected. In such instances formal requests for data will need to be made in writing to the Co-CI's who will discuss this with the TMG. In the event of publications arising from such analyses, those responsible will need to provide the CI with a copy of any intended manuscript for approval prior to submission. Authorship will need to take the format of "[name] on behalf of the TEST-IT Clinical Trial Group" or something similar which will be agreed by the TMG.

